### 3. Scoliosis Patient Questionnaire

**Scoliosis Patient Questionnaire:  
Version 30 (Encompasses Versions 22 and 24)**

**Modified 11/12/03**

Patient Name: _____	Age: _____	Date: _____		
Medical Record # _____	SS: _____			
Exam: Pre-treatment	3 mos.	6 mos.	1 year	_____ years
Your doctors are carefully evaluating the condition of your back before and after your treatment. Please circle the one best answer to each question unless otherwise indicated. If you already have had surgery, please complete sections 1 and 2. Otherwise, just complete section 1.				

All results will be kept confidential.

**Section 1: All patients**

1. Which one of the following best describes the amount of pain you have experienced during the past 6 months?
 
 None       Moderate to severe  Mild       Severe  Moderate
 
2. Which one of the following best describes the amount of pain you have experienced over the last month?
 
 None       Moderate to severe  Mild       Severe  Moderate
 
3. During the past 6 months have you been a very nervous person?
 
 None of the time       Most of the time  A little of the time       All of the time  Some of the time
 
4. If you had to spend the rest of your life with your back shape as it is right now, how would you feel about it?
 
 Very happy       Somewhat unhappy  Somewhat happy       Very unhappy  Neither happy nor unhappy
 
5. What is your current level of activity?
 
 Bedridden/wheelchair  Primarily no activity  Light labor, such as household chores  Moderate manual labor and moderate sports, such as walking and biking  Full activities without restriction
 
6. How do you look in clothes?
 
 Very good  Good  Fair  Bad  Very bad
	
7. In the past 6 months have you felt so down in the dumps that nothing could cheer you up?
 
 Very often       Rarely  Often       Never  Sometimes
 
8. Do you experience back pain when at rest?
 
 Very often       Rarely  Often       Never  Sometimes
 
9. What is your current level of work/school activity?
 
 100% normal       25% normal  75% normal       0% normal  50% normal
 
10. Which of the following best describes the appearance of your trunk; defined as the human body except for the head and extremities?
 
 Very good       Poor  Good       Very poor  Fair
 
11. Which one of the following best describes your medication usage for your back?
 
 None  Non-narcotics weekly or less (e.g., Tylenol, Ibuprofen)  Non-narcotics daily  Narcotics weekly or less (e.g., Percocet, Lorcet, Codeine, Darvocet)  Narcotics daily  Other (please specify below)
 
Medication: _____
 
Usage (weekly or less or daily): _____

--	---

12. Does your back limit your ability to do things around the house?

 Never	 Often
 Rarely	 Very often
 Sometimes	

13. Have you felt calm and peaceful during the past 6 months?

 All of the time	 A little of the time
 Most of the time	 None of the time
 Some of the time	

14. Do you feel that your back condition affects your personal relationships?

 None	 Moderately
 Slightly	 Severely
 Mildly	

15. Are you and/or your family experiencing financial difficulties because of your back?

 Severely	 Slightly
 Moderately	 None
 Mildly	

16. In the past 6 months have you felt down-hearted and blue?

 Never	 Often
 Rarely	 Very often
 Sometimes	

17. In the last 3 months have you taken any sick days from work/school due to back pain and, if so, how many?

0     1     2     3     4 or more

18. Do you go out more or less than your friends?

 Much more	 Less
 More	 Much less
 Same	

19. Do you feel attractive with your current back condition?

 Yes, very	 No, not very much
 Yes, somewhat	 No, not at all
 Neither attractive nor unattractive	

20. Have you been a happy person during the past 6 months?

 None of the time	 Most of the time
 A little of the time	 All of the time
 Some of the time	

21. Are you satisfied with the results of your back management?

 Very satisfied	 Unsatisfied
 Satisfied	 Very unsatisfied
 Neither satisfied nor unsatisfied	

22. Would you have the same management again if you had the same condition?

 Definitely yes	 Probably not
 Probably yes	 Definitely not
 Not sure	

23. On a scale of 1 to 9, with 1 being very low and 9 being extremely high, how would you rate your self-image?

1     2     3     4     5     6     7     8     9

## Section 2: Post-surgery patients only

24. Compared with before treatment, how do you feel you now look?

 Much better	 Worse
 Better	 Much worse
 Same	

25. Has your back treatment changed your function and daily activity?

Increased     Not changed     Decreased

26. Has your back treatment changed your ability to enjoy sports/hobbies?

Increased     Not changed     Decreased

27. Has your back treatment \_\_\_\_\_ your back pain?

Increased     Not changed     Decreased

28. Has your treatment changed your confidence in personal relationships with others?

Increased     Not changed     Decreased

29. Has your treatment changed the way others view you?

[figure not shown]
[figure not shown]
 Much better	 Worse
 Better	 Much worse
 Same	

30. Has your treatment changed your self-image?

Increased     Not changed     Decreased

*Please mark on the drawings any areas where you feel pain. If you are not having any pain, leave blank and initial.*

*Use the following key to show particular types of pain*

#### 4. Adverse Event (AE) Report Form

STUDY NAME:

Site Number: \_\_\_\_\_

Pt\_ID: \_\_\_\_\_

Has the participant had any Adverse Events during this study?  Yes  No (If yes, please list all Adverse Events below)

Severity	Study Intervention Relationship	Action Taken Regarding Study Intervention	Outcome of AE	Expected	Serious
1 = Mild 2 = Moderate 3 = Severe	1 = Definitely related 2 = Possibly related 3 = Not related	1 = None 2 = Discontinued permanently 3 = Discontinued temporarily 4 = Reduced Dose 5 = Increased Dose 6 = Delayed Dose	1 = Resolved, No Sequel 2 = AE still present- no treatment 3 = AE still present-being treated 4 = Residual effects present-not treated 5 = Residual effects present- treated 6 = Death 7 = Unknown	1 = Yes 2 = No	1 = Yes 2 = No (If yes, complete SAE form)

Adverse Event	Start Date	Stop Date	Severity	Relationship to Study Treatment	Action Taken	Outcome of AE	Expected?	Serious Adverse Event?	Initials
1.									
2.									
3.									

## 5. Serious Adverse Event (SAE) Report Form

**Protocol Title:**

**Protocol Number:** \_\_\_\_\_

**Site Number:** \_\_\_\_\_

**Pt\_ID:** \_\_\_\_\_

1. SAE Onset Date: \_\_\_\_\_ (dd/mm/yyyy)

2. SAE Stop Date: \_\_\_\_\_ (dd/mm/yyyy)

3. Location of serious adverse event: \_\_\_\_\_

4. Was this an unexpected adverse event? Yes  No

5. Brief description of participant(s) with no personal identifiers:

Sex: F  M  Age: \_\_\_\_\_

6. Brief description of the nature of the serious adverse event (attach description if more space needed):  
\_\_\_\_\_  
\_\_\_\_\_

7. Category of the serious adverse event:

death – date \_\_\_/\_\_\_/\_\_\_(dd/mmm/yyyy)  
 life-threatening  
 hospitalization-initial or prolonged  
 disability / incapacity

congenital anomaly / birth defect  
 required intervention to prevent permanent impairment  
 other: \_\_\_\_\_

8. Intervention type:

Medication or Nutritional Supplement: specify \_\_\_\_\_  
 Device: Specify: \_\_\_\_\_  
 Surgery: Specify: \_\_\_\_\_  
 Behavioral/Life Style: Specify: \_\_\_\_\_

9. Relationship of event to intervention:

- Unrelated (clearly not related to the intervention)
- Possible (may be related to intervention)
- Definite (clearly related to intervention)

10. Was study intervention discontinued due to event?  Yes  No

11. What medications or other steps were taken to treat serious adverse event?

---

---

12. List any relevant tests, laboratory data, history, including preexisting medical conditions

---

---

13. Type of report:

- Initial
- Follow-up
- Final

Signature of Principal Investigator: \_\_\_\_\_ Date: \_\_\_\_\_

# Hyperkyphosis Telephone Screen

Please complete the survey below.

Thank you!

Participant ID: \_\_\_\_\_

Acrostic: \_\_\_\_\_

Interviewer: \_\_\_\_\_

How was person contacted: \_\_\_\_\_

- Physician referral
- Previous pilot
- Recruitment letter
- Flyer
- Personal referral

Physician name: \_\_\_\_\_

Where did you see the flyer? \_\_\_\_\_

Subject Name: \_\_\_\_\_

((Please spell))

Telephone: home \_\_\_\_\_

cell phone number: \_\_\_\_\_

Are you 60 years of age or older? \_\_\_\_\_

- Yes
- No

Can you comfortably communicate in English with verbal and written communication? \_\_\_\_\_

- Yes
- No

Have you or a family member or friend noticed that you do not stand as straight and tall as you used to? \_\_\_\_\_

- Yes
- No

Are you able to walk inside without a cane or walker? \_\_\_\_\_

- Yes
- No

Are you able to walk  $\frac{1}{4}$  block without using a cane or a walker? \_\_\_\_\_

- Yes
- No

Are you able to climb one flight of stairs independently - without assistance from another person? \_\_\_\_\_

- Yes
- No

Are you able to rise from a chair with your arms crossed at your chest? \_\_\_\_\_

- Yes
- No

Are you able to straighten your upper back? \_\_\_\_\_

- Yes
- No

Do you have any chronic medical conditions such as: \_\_\_\_\_

A painful fracture of your vertebra (spine) in the past 3 months? \_\_\_\_\_

- Yes
- No

Total hip or knee replacement, or hip fracture in past 6 mos. \_\_\_\_\_

- Yes
- No

Oral glucocorticoid medications (steroids)  $\geq 3$  months in the past year \_\_\_\_\_

- Yes
- No

Uncontrolled hypertension, chest pain, myocardial infarct within past 6 months)	 Yes  No
Peripheral neuropathy in your arms or legs	 Yes  No
Diagnosed vestibular or neurologic disorder	 Yes  No
Unexplained weight loss (>10 pounds in the past year)	 Yes  No
Have you fallen 3 or more times in the past year?	 Yes  No
Do you have any chronic medical conditions that could prevent you from participating in an exercise program?	 Yes  No
Have you been advised by a physician not to exercise?	 Yes  No
Do you already engage in regular (at least 3 days/week) vigorous (at least 30 continuous minutes) exercise that includes spine strengthening exercise?	 Yes  No
Do you have a current major uncontrolled psychiatric illness, cognitive impairment or substance abuse?	 Yes  No
Do you have plans to move out of the area within the next 6 months?	 Yes  No
Are you interested in participating in a study that meets three times a week for 6 months for one hour of group exercise?	 Yes  No
Are you interested in participating in a study that meets twice a week for 3 months for one hour of group exercise?	 Yes  No
Which location would you prefer to attend the exercise classes (check all that apply):	 Osher Center on [name]?  UCSF Department of Physical Therapy and Rehabilitation Health and Wellness Center at Mission Bay?  Kaiser Permanente - French Campus on [name]  SF VA Medical Center on [name]
Do you have a friend or partner you want to be in the study with?	 Yes  No
Who is this person?	_____
What is your address?	_____
City:	_____

State:

- AL
- AK
- AZ
- AR
- CA
- CO
- CT
- DE
- FL
- GA
- HI
- ID
- IL
- IN
- IA
- KS
- KY
- LA
- ME
- MD
- MA
- MI
- MN
- MS
- MO
- MT
- NE
- NV
- NH
- NJ
- NM
- NY
- NC
- ND
- OH
- OK
- OR
- PA
- RI
- SC
- SD
- TN
- TX
- UT
- VT
- VA
- WA
- WV
- WI
- WY

Zip code

---

What is the best phone number to reach you at?

---

What is your date of birth?

---

What is the name of an emergency contact for you?

---

What is the phone number of an emergency contact for you?

---

Do we have permission to contact your provider about your participation in the study? if no, advise this is required for study participation

- Yes
- No

Name of primary physician, nurse practitioner or physician's assistant:

---

Address: \_\_\_\_\_

City: \_\_\_\_\_

State: \_\_\_\_\_

- AL
- AK
- AZ
- AR
- CA
- CO
- CT
- DE
- FL
- GA
- HI
- ID
- IL
- IN
- IA
- KS
- KY
- LA
- ME
- MD
- MA
- MI
- MN
- MS
- MO
- MT
- NE
- NV
- NH
- NJ
- NM
- NY
- NC
- ND
- OH
- OK
- OR
- PA
- RI
- SC
- SD
- TN
- TX
- UT
- VT
- VA
- WA
- WV
- WI
- WY

Zip code: \_\_\_\_\_

Phone number: \_\_\_\_\_

Are you available to come into UCSF Parnassus for a  
clinical screening exam?

- Yes
- No

Provide them with a screening appointment

Why not?

- Not interested in study
- Other

Would you like to be contacted about future studies?

Yes  
 No

What is the best phone number to reach you at in the future?

---

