**TABLE 1. CHANGE IN KYPHOSIS, STRENGTH, AND PHYSICAL FUNCTION AFTER 12-WEEKS**

Kyphosis	change $\pm$ sd	p-value
Debrunner kyphosis (degrees)	$-6 \pm 3$	$< .001^*$
Strength		
Biodex spinal extensor strength (% body weight)	$21 \pm 13$	$< .001^*$
Physical function		
Jug test (seconds)	$-1.4 \pm 1.3$	$.001^*$
Modified Physical Performance Test (36-points)	$2 \pm 2$	$.001^*$
Gait speed (meters/second)	$0.05 \pm 0.10$	.06

\*p<0.05

**Feasibility and retention in the pilot trial:** It was feasible to recruit participants for the pilot trial, screen by telephone and a clinic screening visit, and enroll prior to a baseline examination. Our recruitment methods included posting flyers at local clinics, hospitals, and senior community centers. Over 1 year, we screened a total of 189 people by phone, of whom 93 (49%) were eligible to attend the screening visit. Of these eligible participants, 92 (48%) attended the clinic screening visit, which included measurement of kyphosis and a cognitive screening exam. A total of 36 (39%) persons screened at the clinic visit fulfilled study eligibility criteria and were invited to enroll in the study. Eleven (30%) declined participation, and 25 participants were enrolled in the study. Four participants withdrew during the study, 3 due to nonstudy-related injuries and 1 withdrew because of a family emergency. Of the 25 enrolled in the study, 21 (84%) completed the trial.

**Adherence in the pilot trial:** we measured adherence to the exercise intervention by attendance at the classes and by self-reported frequency of practice of home spinal alignment. We requested that all participants enrolled attend 24 classes over the course of the 12-week pilot trial; we provided four make-up classes to accommodate absences. We requested that participants practice ideal spinal alignment 3 times a day. Each participant was given a log in which to record each practice session.

**Adherence to group exercise classes** was exceptional. Other than those who withdrew because of unrelated injuries or family emergency, all participants completed 24 sessions and exceeded the required 3-times-per-day home spinal alignment practice. Participants were asked for feedback about the study at the 1-year follow-up visit, and all reported a newfound sense of confidence walking with improved spinal alignment.

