## **4. SELECTION AND ENROLLMENT OF PARTICIPANTS**

### **4.1 and 4.2 Inclusion and Exclusion Criteria**

**Study participants.** The study population consists of 100 community-dwelling men and women aged 60 years and older with kyphosis  $\geq 40$  degrees measured by Debrunner kyphometer (Proteck AG, Berne, Switzerland), a protractor-like tool placed over the T4 and T12 spinous processes to measure kyphosis externally.

**Eligibility criteria:** Participant eligibility will be assessed with a telephone interview, a clinical screening visit, and subsequently during a telephone screening with the participant's primary care provider. If the participant's primary care provider does not approve participation, or if they do not have a provider, and is unwilling to see a primary care provider, they will be excluded from the study.

We will exclude for: 1) advanced disability or end-stage disease, 2) no active movement in thoracic spine, 3) unable to execute exercise safety tests, 4) failure to comply with run-in procedures: poor attendance, non-compliant with wearing a pedometer, 5) major psychiatric illness, cognitive impairment, or substance abuse, 6) uncontrolled hypertension, diagnosed vestibular or neurologic disorder, total hip or knee replacement or hip fracture within the previous 12 months, oral glucocorticoid medications for 6 weeks or more the past year, unexplained weight loss ( $>10$  pounds in the past year), gait speed  $<0.6$  m/s, painful vertebral fractures in the past 6 months or 3 or more falls in the past year, and 7) non-English speaking.

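### The telephone screen uses looser limits than Section 4 for three exclusions, and no later form in the appendix restores them

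*Combined protocol and SAP*

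**What the plan says.** Section 4.1 and 4.2 sets the limits. It excludes "painful vertebral fractures in the past 6 months" and also "total hip or knee replacement or hip fracture within the previous 12 months, oral glucocorticoid medications for 6 weeks or more the past year".

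The Hyperkyphosis Telephone Screen (Appendix III, item 6) asks about the same three matters with different limits. The vertebral item reads "A painful fracture of your vertebra (spine) in the past 3 months". The hip and knee item reads "Total hip or knee replacement, or hip fracture in past 6 mos". The steroid item counts use of 3 months or longer in the last year.

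Eligibility is also examined after the call. Section 6.2 has a study physician review the medical criteria and contact the primary care provider. Section 4 excludes a person if the "primary care provider does not approve participation". The Procedures Schedule (Appendix I) marks eligibility criteria at the telephone, clinic and medical screens, and marks medical history and current medications again at the medical screen.

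**The concern.** All three differences run in the same direction: the form passes people whom Section 4 excludes. Staff who follow it as written would book them for the clinic visit. Unless a later step asks for the date of the event or the length of the steroid course, nothing on paper would stop enrolment.

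The plan does not state why these exclusions were chosen, but a safety purpose is the natural reading. Section 5.1 and Table 2 describe prone trunk lifts and spinal extensor strengthening that progresses to 70-80% intensity, in people aged 60 or older. A recent painful vertebral fracture bears directly on that load.

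There is a reporting consequence too. Section 7.2 requires the annual report to say whether everyone enrolled was eligible. For these three criteria the forms in the appendix could not support that statement.

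**Working it through.** The plan gives no figure to reproduce here, so the check sets the texts side by side and works out the gap.

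**Limits compared**

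| Exclusion | Section 4 | Telephone screen | Excluded by Section 4 but passed by the form |
|---|---|---|---|
| Painful vertebral fracture | 6 months | 3 months | more than 3 and up to 6 months ago |
| Hip fracture, hip or knee replacement | 12 months | 6 months | more than 6 and up to 12 months ago |
| Oral glucocorticoids in the last year | 6 weeks or more | 3 months or more | 6 weeks to just under 3 months of use |

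Share of the window covered: 3/6 = 50% for vertebral fracture and 6/12 = 50% for the hip and knee events. For steroids, 3 months is about 13 weeks, so the missed band is about 13 − 6 = 7 weeks wide.

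**Do later forms close the gap?**

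- *Steroids.* The Clinic Screening Exam asks only about more than 3 months of continuous use, which is looser again. The Medications Inventory asks what the person takes now, so a finished 8-week course need not appear. If it did, a single duration class runs from 1 month to 1 year and cannot separate less than 6 weeks from more.
- *Fractures.* The Clinic Screening Exam records the site (spine and hip are options) but neither the date nor whether a spine fracture was painful. The Medical History form has no fracture item.
- *Joint replacement.* The Medical History form records the calendar year only.
- *Clinic visit.* The criteria that Sections 4.3 and 6.2 name for this visit are kyphosis, thoracic movement, gait speed and safety tests. None of the three exclusions is among them.

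**How much does a year-only date resolve?** Consider operations 6 to 12 months before screening, the band the telephone item misses. Assume the screening time T is uniform over the calendar year (0 to 1) and the operation took place u years earlier, with u uniform on 0.5 to 1. The recorded year is the current one only if T > u.

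- Share with the current year, clearly inside 12 months: mean(1 − u) = 1 − 0.75 = 0.25.
- Share with the previous year, which cannot be placed: mean(u) = 0.75.

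So about a quarter of these operations could be identified from the form and about three quarters could not.

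**Is the form a deliberately coarse first filter?** Its items on weight loss, falls and vestibular or neurologic disorder use the Section 4 limits, so it does apply Section 4 elsewhere. It also asks about interest in "a study that meets twice a week for 3 months for one hour of group exercise". This trial meets three times a week for 6 months. The pilot, described in Section 2.2, did match that question: "We requested that all participants enrolled attend 24 classes over the course of the 12-week pilot trial", and 24/12 = 2 classes a week for about 3 months. That suggests, without proving, that the three limits came from earlier work and were not updated.

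**The case against.** The best answer is that the telephone screen admits nobody; it only leads to a clinic appointment. Section 4 governs throughout, a physician reviews medical criteria before enrolment, and the primary care provider can veto. The appendix contains no eligibility checklist and no form for the provider contact, so the step that decides medical eligibility cannot be judged from the documents. This stands as a limit on the finding: enrolling an ineligible person is a risk, not a certainty. It does not make the limits on the telephone form right, and no form shown gives the physician the missing dates or durations.

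Other protections exist. The telephone form asks about conditions that would prevent exercise and about medical advice against it. The clinic steroid and fracture items may be meant as risk-factor history. A reviewer who sees a steroid listed, or last year's date, can ask more. These may catch some people, but none applies the Section 4 limits.

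On safety, training starts without resistance and reaches high intensity after about 10 weeks (Section 5.1). A fracture just over 3 months old at the call would then be at least about 3 + 2.3 = 5.3 months old. That reduces the concern about peak load, but the unloaded and lighter exercises begin earlier. Baseline radiographs are not listed as an eligibility step.

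The carry-over explanation is open to doubt, because the same form also states this trial's own schedule correctly. The finding does not depend on it.

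Finally, the form limits might be the intended ones. Section 4 is the governing eligibility text, so the forms should follow it unless the investigators decide otherwise and amend it. The two cannot both stand.

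**Conclusion.** The concern holds. Three decision limits on the telephone screen are wrong relative to Section 4, all in the looser direction. The form covers half of the required window for vertebral fracture and half for the hip and knee events, and it misses steroid courses of 6 to just under about 13 weeks. No later form in the appendix applies the Section 4 limits.

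These comparisons need no assumption. The 25%/75% split for joint replacement dates does: it rests on evenly spread dates and concerns one field. The conclusion about later forms covers only those in the appendix. The documents give no frequencies, so the number of ineligible people who would pass is unknown.

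The consequence is for participant safety and for documenting eligibility. The treatment comparison, type I error and power calculation are unaffected. It should be corrected, because the exclusions bear on a loaded spinal extension programme and the correction is cheap.

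**What to change.** Leave Section 4 as it is and bring the forms into line with it.

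- **Telephone Screen:** ask about painful vertebral fracture over 6 months, hip fracture and hip or knee replacement over 12 months, and oral glucocorticoids taken for at least 6 weeks in the last year.
- **Clinic Screening Exam:** use the same steroid threshold, and add month and year to the fracture item.
- **Medical History:** record month as well as year for joint replacement.

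The cost is edits to three electronic forms and IRB approval of the change under Section 11.1. No visit or procedure is added. Nobody eligible under Section 4 is lost, since the new limits remove only people whom Section 4 already excludes, and some clinic visits by ineligible callers are avoided.
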